8.0 Dosage Modification Based on Adverse Events

Strictly follow the modifications in this table for the first **two** cycles, until individual treatment tolerance can be ascertained. Thereafter, these modifications should be regarded as guidelines to produce mild-to-moderate, but not debilitating, side effects. If multiple adverse events are seen, administer dose based on greatest reduction required for any single adverse event observed. Reductions or increases apply to treatment given in the preceding cycle and are based on adverse events observed since the prior dose.

ALERT: ADR reporting may be required for some adverse events (See Section 10)

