8.1 Dose Levels (Based on Adverse Events in Tables 8.2)

Brentuximab Vedotin	
	Starting Dose 1.8 mg/kg IV Day 1
1 st dose reduction	1.2 mg/kg IV Day 1
2 nd dose reduction	Discontinue

Nivolumab	
	Starting Dose 3.0 mg/kg IV Day 1
1 st dose reduction	Discontinue

Note: If either drug is discontinued, the patient may continue treatment with the other drug. If both drugs are discontinued, the patient will go to event monitoring per Section 18.0.

8.2 **Recommended Brentuximab Vedotin (BV) and Nivolumab Dose Modifications for Treatment-Associated Toxicity**

→ → Use the NCI Common Terminology Criteria for Adverse Events (CTCAE) version 4.0* unless otherwise specified ← ←			
CTCAE System/Organ/Class (SOC)	ADVERSE EVENT	AGENT	ACTION**
AT TIME OF RETREATMENT			
Investigations	Platelet count decreased	Brentuximab Vedotin (BV) and Nivolumab	Grade 3: Hold both BV and nivolumab until grade 2 or better, then reinstitute BV at 1.2 mg/kg and resume nivolumab at same dose.

→ → Use the NCI Common Terminology Criteria for Adverse Events (CTCAE) version 4.0* unless otherwise specified ← ←			
CTCAE System/Organ/Class (SOC)	ADVERSE EVENT	AGENT	ACTION**
Investigations	
Alanine aminotransferase Increased, Aspartate aminotransferase Increased, and/or Blood bilirubin increased
 
NOTE: increased bilirubin does not factor into dose modifications if secondary to Gilbert's syndrome.
	Brentuximab Vedotin (BV) and Nivolumab	
Grade 2 (>3 to 5 x ULN) AST or ALT elevations: Omit dosing for nivolumab; continue BV at the same dose level. Nivolumab may be resumed if the value improves to Grade 1 (≤ 3 x ULN) or better.
 
Grade 2 Bilirubin elevations (>1.5 to 3 x ULN): Omit dosing for nivolumab; continue BV at the same dose level. Nivolumab may be resumed if the bilirubin improves to Grade 1 (>ULN to 1.5 x ULN) or better.
 
Grade 2 (>3 to 5 x ULN) AST or ALT elevations WITH Grade 2 Bilirubin elevations (>1.5 to 3 x ULN): Hold both nivolumab and BV until ALT/AST value improves to Grade 1 (≤ 3 x ULN) or better and bilirubin value improves to Grade 1 (>ULN to 1.5 x ULN) or better.
 
Grade 3 (AST or ALT, OR Bilirubin elevations): Discontinue nivolumab; hold dosing for BV until toxicity is \leq Grade 2 or has returned to baseline, then resume at the same dose level.
 
Grade 4 (AST or ALT, OR Bilirubin elevations): Discontinue both nivolumab and BV. Patient should go to event monitoring, per Section 18.

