→ → Use the NCI Common Terminology Criteria for Adverse Events (CTCAE) version 4.0* unless otherwise specified ← ←			
CTCAE System/Organ/Class (SOC)	ADVERSE EVENT	AGENT	ACTION**
Investigations	Creatinine Increased	Nivolumab	
Patients will be monitored for elevated serum creatinine prior to and periodically during treatment. Administer corticosteroids at a dose of 1 to 2 mg/kg/day prednisone equivalents followed by corticosteroid taper for life-threatening (Grade 4) serum creatinine elevation and permanently Discontinue nivolumab; continue BV at the same dose level.
 
For severe (Grade 3) or moderate (Grade 2) serum creatinine elevation, withhold nivolumab and administer corticosteroids at a dose of 0.5 to 1 mg/kg/day prednisone equivalents followed by corticosteroid taper; if worsening or no improvement occurs, increase dose of corticosteroids to 1 to 2 mg/kg/day prednisone equivalents and permanently Discontinue nivolumab; continue BV at the same dose level.

Investigations	Neutrophil (ANC) count decreased	Brentuximab Vedotin (BV) and Nivolumab	
≥Grade 3; hold both BV and nivolumab until resolved to grade 1 (or baseline). At this point myeloid growth factors can be used at investigator's discretion.
 
If not resolved to ≤Grade 1 or better within 28 days, discontinue nivolumab and BV. Patient should go to event monitoring per Section 18.

→ → Use the NCI Common Terminology Criteria for Adverse Events (CTCAE) version 4.0* unless otherwise specified ← ←			
CTCAE System/Organ/Class (SOC)	ADVERSE EVENT	AGENT	ACTION**
	Amylase and/or lipase increase	Brentuximab Vedotin (BV) and Nivolumab	Grade ≥ 3: Hold BV and nivolumab until resolved to ≤Grade 2, then resume at same dose, per protocol. If there is clinical or radiographic evidence of pancreatitis, refer to pancreatitis AE actions (below).

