All other hematologic and non-hematologic	All other hematologic and non-hematologic	Brentuximab Vedotin (BV) and Nivolumab	Grade ≥ 2: Hold both BV and Nivolumab up to four weeks until resolution to Grade 1 or baseline. If no resolution patient should go to event monitoring, per Section 18.

* Located at http://ctep.cancer.gov/protocolDevelopment/electronic_applications/ctc.htm

** Use the following to describe actions in the Action column:

- Omit = The current dose(s) for the specified drug(s) during a cycle is skipped. The patient does not make up the omitted dose(s) at a later time.
- Hold/Delay = The current dose(s) of all drugs during a cycle is delayed. The patient does make up the delayed dose(s) when the patient meets the protocol criteria to restart drugs.
- Discontinue = The specified drug(s) are totally stopped.

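### For a creatinine rise coded alone, Table 8.2 continues BV unchanged at Grade 4 and at Grade 3 that does not improve on corticosteroids, although Section 15.15 links severe renal impairment to BV exposure

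*Combined protocol and SAP*

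**What the plan says.** Table 8.2 (Section 8.2) has a row for increased creatinine with nivolumab as its only agent.

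- **Grade 4:** corticosteroids are given for "life-threatening (Grade 4) serum creatinine elevation and permanently Discontinue nivolumab; continue BV at the same dose level".
- **Grade 3, first step:** nivolumab is withheld and corticosteroids are given. BV is not mentioned.
- **Grade 3, worsening or not improving:** the steroid dose goes up to 1 to 2 mg/kg/day "prednisone equivalents and permanently Discontinue nivolumab; continue BV at the same dose level".

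The row treats Grade 2 like Grade 3; Grade 2 is outside this point.

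Two rules in Section 8.0 set the force of the table. It opens with "Strictly follow the modifications in this table for the first" two cycles, and the actions are guidelines after that. It also states: "If multiple adverse events are seen, administer dose based on greatest reduction required for any single adverse event observed".

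Section 15.15 covers BV in renal impairment. With CrCl below 30 mL/min it reports a trend to moderately lower conjugate exposure and higher exposure to MMAE, the cytotoxic component. It recommends a starting dose of 1.2 mg/kg for that group, unless the study protocol specifies otherwise.

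**The concern.** A patient with a Grade 4 creatinine rise very probably has CrCl below 30 mL/min. The only instruction for BV in the row is to carry on unchanged, which means 1.8 mg/kg unless the dose has already been reduced. That is the group in which the protocol's own drug information expects more MMAE and recommends starting at the lower dose.

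The action also depends on the recorded term. Acute renal failure and nephritis have no row of their own, and Section 15.27 lists both separately from increased creatinine. Recorded at Grade 2 or higher, they fall under the catch-all row: "Hold both BV and Nivolumab up to four weeks until resolution to Grade 1 or baseline". The greatest-reduction rule then holds BV. The same injury recorded only as increased creatinine, even at Grade 4, leaves BV running. If creatinine had no row, BV would be held.

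What is at stake is patient safety. The primary endpoint, sample size, error rates and decision rules are untouched.

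**Working it through.** The plan gives no figure to reproduce. The check has two parts: the BV action by row, then where CrCl is likely to lie at the grades concerned.

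**BV action by row of Table 8.2**

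| Row | Grade 3 | Grade 4 |
|---|---|---|
| Creatinine | First step: none stated. Worsening or not improving: continue | Continue |
| AST, ALT or bilirubin | "Discontinue nivolumab; hold dosing for BV until toxicity is" Grade 2 or lower or baseline, then same dose | "Grade 4 (AST or ALT, OR Bilirubin elevations): Discontinue both nivolumab and BV" |
| Catch-all (acts from Grade 2) | Hold up to four weeks | Hold up to four weeks |
| Immune-mediated rash | Continue | Continue |
| Endocrine (Grade 3 or higher) | Continue | Continue |

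Immune-mediated encephalitis, which the table does not grade, also continues BV. The catch-all covers only events without their own row, so it does not override the creatinine row.

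**Creatinine clearance at the grade floors**

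The formula is in Section 3.12: CrCl = (140 - age) x weight / (72 x creatinine), times 0.85 for women. The documents do not print the creatinine grade cut-offs, so these are assumptions:

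- Grade 3 starts at 3 x ULN (range 2.5 to 3.5).
- Grade 4 starts at 6 x ULN (range 5 to 7).
- ULN is 1.2 mg/dL (range 1.0 to 1.4).

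For a man of 70 years and 75 kg the numerator is 70 x 75 = 5250.

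- Grade 3 floor, base: 5250 / (72 x 3.6) = 20.3 mL/min. Range: 5250 / (72 x 4.9) = 14.9 to 5250 / (72 x 2.5) = 29.2.
- Grade 4 floor, base: 5250 / (72 x 7.2) = 10.1. Range: 5250 / (72 x 9.8) = 7.4 to 5250 / (72 x 5.0) = 14.6.

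Share of an unweighted grid (ages 60 to 80 in 1-year steps, 50 to 100 kg in 1-kg steps) with CrCl below 30 mL/min:

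| Case | Men | Women |
|---|---|---|
| Grade 3 floor, 3 x ULN 1.2 (base) | 99.4% | 100% |
| Grade 3 floor, 3 x ULN 1.0 | 83.9% | 98.8% |
| Grade 3 floor, 2.5 x ULN 1.0 (mildest) | 55.4% | 81.2% |
| Grade 4 floor, every combination | 100% | 100% |

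The highest Grade 4 value is at age 60 and 100 kg with 5 x ULN 1.0: 80 x 100 / (72 x 5.0) = 22.2.

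If Grade 3 is counted from 3 x baseline instead, the same 70-year-old man has:

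- baseline 0.7: 5250 / (72 x 2.1) = 34.7
- baseline 0.8: 5250 / (72 x 2.4) = 30.4
- baseline 1.0: 5250 / (72 x 3.0) = 24.3

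So below 30 mL/min is firm at Grade 4 and frequent, but not certain, at Grade 3. Cockcroft-Gault is only illustrative while creatinine is still rising.

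**Size of the dose and reach of the rule**

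At 75 kg, 1.8 x 75 = 135 mg against 1.2 x 75 = 90 mg. Cycles 2 to 8 give 7 retreatment doses. The table strictly binds 1 of them (cycle 2), or 2 if events in cycle 2 also bind the cycle 3 dose. For the rest it is guidance.

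**The case against.** The strongest defence is attribution. The creatinine row is built as an immune-mediated nivolumab row: treat with corticosteroids, act on nivolumab, leave BV alone. The rash, encephalitis and endocrine rows follow the same pattern. BV's toxicity list in Section 15.17 has hepatic but no renal terms, so treating liver and kidney differently is coherent, and the liver row is an imperfect comparator. A specific row is also entitled to depart from the catch-all. All of this stands. It explains the row, but it does not settle whether unchanged BV is suitable at a CrCl near 10. Section 15.15 ties kidney function to BV exposure whatever the cause, and the documents give no such link for rash, encephalitis or endocrine events.

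The pharmacology is modest: a trend, with MMAE recovered 72% in feces and 27% in urine. The 1.2 mg/kg figure is a starting dose. Nor does the protocol lower the entry dose for low CrCl. The floor of 30 in Section 3.12 applies only to patients under 60 qualifying on renal function; older patients need creatinine of at most 2.0 mg/dL (Section 3.16). A man of 80 years and 60 kg at 2.0 has CrCl 60 x 60 / (72 x 2.0) = 25 and starts at 1.8 mg/kg. The fix must therefore not cut such a patient once he is back at baseline.

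A reader might infer that the row contradicts Section 15.15. It does not, because that section defers to the protocol. A reader might also infer that every Grade 3 rise continues BV by instruction. The first step gives none. The footnote to Table 8.2 defines a hold as delaying all drugs, and the row's verb, withhold, is undefined, so that step is ambiguous.

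Finally, the gap is narrow. It closes when a second recorded event holds BV, and Section 13.3 lets a patient leave treatment for unacceptable adverse events, though that is removal and not a hold rule. Appendix V, cited in Section 9.6, was not available, so a renal instruction there cannot be excluded.

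**Conclusion.** The point holds as an inconsistency in dosing guidance that is cheap to repair. For a creatinine rise coded alone, the table continues BV unchanged at Grade 4 and at Grade 3 that worsens or does not improve on corticosteroids. Grade 4 is the firm part: every grid case lies below 30 mL/min. For Grade 3 the statement is often, given 55% of male points in the mildest case and values of 30 to 35 under baseline-referenced grading with low baselines.

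This rests on the assumed CTCAE cut-offs and ULN, on an unweighted grid that describes no actual population, and on Appendix V not saying otherwise. No frequency is claimed, because the documents give no rate of Grade 3 or 4 creatinine increase. A reader might infer that full-dose BV has been shown to be harmful here; the documents support only a trend in exposure and a lower recommended starting dose. Confidence is medium, and the change is advisable but not essential.

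**What to change.** List BV as an agent in the creatinine row. For Grade 4, and for Grade 3 that worsens or does not improve, replace the instruction to continue BV with:

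*Hold BV until creatinine is Grade 2 or lower or back to baseline. Then resume at the same dose if CrCl (Cockcroft-Gault) is at least 30 mL/min or has returned to its baseline value; otherwise resume at 1.2 mg/kg. If not recovered within four weeks, consult the PI on whether to continue BV.*

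The pieces already exist: the 1.2 mg/kg level (Section 8.1), the formula (Section 3.12), creatinine before each cycle (Section 4.0), the catch-all's four-week limit and, in the neuropathy row, consultation with the PI. Resuming at a lower dose goes beyond the liver row, but the platelet row has the precedent: "then reinstitute BV at 1.2 mg/kg and resume nivolumab at same dose".

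Two checks. The man of 70 years and 75 kg, recovered to Grade 2, resumes at the same dose if creatinine is at most 70 x 75 / (72 x 30) = 2.43 mg/dL, or if his CrCl is back to baseline. The man of 80 years and 60 kg, back at his baseline CrCl of 25, resumes at the dose he was on.

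The cost is one table row, a delayed cycle or lower BV dose intensity in affected patients, and an interruption of all protocol therapy where nivolumab has already been stopped, as the row requires in both situations. Compulsory BV discontinuation at four weeks is avoided, because under the Section 8.1 note it would then end protocol treatment. Grade 2 stays as written, so the change reduces but does not remove dependence on the coded term. Check Appendix V for agreement at the same time.

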9.0 Ancillary Treatment/Supportive Care

9.1 Antiemetics may be used at the discretion of the attending physician.

9.2 Blood products and growth factors should be utilized as clinically warranted and following institutional policies and recommendations. The use of growth factors is discouraged but if necessary should follow published guidelines of the American Society of Clinical Oncology (ASCO) Update of Recommendation for the Use of White Blood Cell Growth Factors: An Evidence-Based Clinical Practice Guideline. J Clin Oncol 2006; 24:3187-3205, 2006.

9.3 Patients should receive full supportive care while on this study. This includes blood product support, antibiotic treatment, and treatment of other newly diagnosed or concurrent medical conditions. All blood products and concomitant medications such as anti-diarrheal, analgesics, and/or antiemetics received from the first day of study treatment administration until 30 days after the final dose will be recorded in the medical records.

- 9.4 Diarrhea: This could be managed conservatively with loperamide. The recommended dose of loperamide is 4 mg at first onset, followed by 2 mg every 2-4 hours until diarrhea free (maximum 16 mg/day).

In the event of grade 3 or 4 diarrhea, the following supportive measures are allowed: hydration, octreotide, and antidiarrheals.

If diarrhea is severe (requiring intravenous rehydration) and/or associated with fever or severe neutropenia (grade 3 or 4), broad-spectrum antibiotics must be prescribed. Patients with severe diarrhea or any diarrhea associated with severe nausea or vomiting **should be hospitalized** for intravenous hydration and correction of electrolyte imbalances.

- 9.5 As there is potential for hepatic toxicity with nivolumab or nivolumab combinations, drugs with a predisposition to hepatotoxicity should be used with caution in patients treated with nivolumab-containing regimen.

- 9.6 Please refer to Appendix V for additional Adverse Event Management Algorithms

10.0 Adverse Event (AE) Reporting and Monitoring

The site principal investigator is responsible for reporting any/all serious adverse events to the sponsor as described within the protocol, regardless of attribution to study agent or treatment procedure. The sponsor/sponsor-investigator is responsible for notifying FDA and all participating investigators in a written safety report of any of the following:

- Any suspected adverse reaction that is both serious and unexpected.
- Any findings from laboratory animal or *in vitro* testing that suggest a significant risk for human subjects, including reports of mutagenicity, teratogenicity, or carcinogenicity.
- Any findings from epidemiological studies, pooled analysis of multiple studies, or clinical studies, whether or not conducted under an IND and whether or not conducted by the sponsor, that suggest a significant risk in humans exposed to the drug.
- Any clinically important increase in the rate of a serious suspected adverse reaction over the rate stated in the protocol or Investigator's Brochure (IB).

Definitions

Adverse Event

Any untoward medical occurrence associated with the use of a drug in humans, whether or not considered drug related.

Suspected Adverse Reaction

Any adverse event for which there is a reasonable possibility that the drug caused the adverse event.

Expedited Reporting

Events reported to sponsor within 24 hours, 5 days or 10 days of study team becoming aware of the event.

Routine Reporting

Events reported to sponsor via case report forms

Events of Interest

Events that would not typically be considered to meet the criteria for expedited reporting, but that for a specific protocol are being reported via expedited means in order to facilitate the review of safety data (may be requested by the FDA or the sponsor).

10.1 Adverse Event Characteristics

CTCAE term (AE description) and grade: The descriptions and grading scales found in the revised NCI Common Terminology Criteria for Adverse Events (CTCAE) version 4.0 will be utilized for AE reporting. All appropriate treatment areas should have access to a copy of the CTCAE version 4.0. A copy of the CTCAE version 4.0 can be downloaded from the CTEP web site:

- a. Adverse event monitoring and reporting is a routine part of every clinical trial.
- b. Identify the grade and severity of the event using the CTCAE version 4.0.
- c. Determine whether the event is expected or unexpected (see Section 10.2).
- d. Determine if the adverse event is related to the study intervention (agent, treatment or procedure) (see Section 10.3).
- e. Determine whether the event must be reported as an expedited report. If yes, determine the timeframe/mechanism (see Section 10.4).
- f. Determine if other reporting is required (see Section 10.5).
- g. Note: All AEs reported via expedited mechanisms must also be reported via the routine data reporting mechanisms defined by the protocol (see Sections 10.5.2 and 18.0).

10.11 Each CTCAE term in the current version is a unique representation of a specific event used for medical documentation and scientific analysis and is a single MedDRA Lowest Level Term (LLT).

NOTE: A severe AE, as defined by the above grading scale, is NOT the same as serious AE which is defined in the table in Section 10.4.

10.2 Expected vs. Unexpected Events

Expected events - are those described within the Section 15.0 of the protocol, the study specific consent form, package insert (if applicable), and/or the investigator brochure, (if

an investigator brochure is not required, otherwise described in the general investigational plan).

Unexpected adverse events or suspected adverse reactions are those not listed in Section 15.0 of the protocol, the study specific consent form, package insert (if applicable), or in the investigator brochure (or are not listed at the specificity or severity that has been observed); if an investigator brochure is not required or available, is not consistent with the risk information described in the general investigational plan.

Unexpected also refers to adverse events or suspected adverse reactions that are

mentioned in the investigator brochure as occurring with a class of drugs but have not been observed with the drug under investigation.

Unanticipated Adverse Device Event (UADE)

Any serious adverse effect on health or safety or any life-threatening problem or death caused by, or associated with, a device, if that effect, problem, or death was not previously identified in nature, severity, or degree of incidence in the investigational plan or application (including a supplementary plan or application), or any other unanticipated serious problem associated with a device that relates to the rights, safety, or welfare of subjects

10.3 Assessment of Attribution

When assessing whether an adverse event is related to a medical treatment or procedure, the following attribution categories are utilized:

Definite - The adverse event *is clearly related* to the agent(s).

Probable - The adverse event *is likely related* to the agent(s).

Possible - The adverse event *may be related* to the agent(s).

Unlikely - The adverse event *is doubtfully related* to the agent(s).

Unrelated - The adverse event *is clearly NOT related* to the agent(s).

Events determined to be possibly, probably or definitely attributed to a medical treatment suggest there is evidence to indicate a causal relationship between the drug/device and the adverse event.

10.31 **AEs Experienced Utilizing Investigational Agents and Commercial Agent(s) on the SAME (Combination) Arm**

When a commercial agent(s) is (are) used on the same treatment arm as the investigational agent/intervention (also, investigational drug, biologic, cellular product, or other investigational therapy under an IND), the **entire combination (arm) is then considered an investigational intervention for reporting.**

10.32 **EXPECTED Serious Adverse Events: Protocol Specific Exceptions to Expedited Reporting**

For this protocol only, the following Adverse Events/Grades are expected to occur within this population and do not require Expedited Reporting. If patient is hospitalized, please follow normal reporting criteria. These events must still be reported via Routine Reporting (see Section 10.52). *

System Organ Class (SOC)	Adverse event/ Symptoms	CTCAE Grade at which the event will not require expedited reporting.
Investigations	Neutrophil count decreased	≤Grade 4
	Platelet count decreased	≤Grade 4
	White blood count	≤Grade 4
	Lymphocyte count decreased	≤Grade 4
Blood and lymphatic system disorders	Anemia	≤Grade 4

*Report any clinically important increase in the **rate** of a serious suspected adverse reaction (at your study site) over that which is listed in the protocol or investigator brochure as an expedited event.

*Report an expected event that is greater in severity or specificity than expected as an expedited event

*An investigational agent/intervention might exacerbate the expected AEs associated with a commercial agent. Therefore, if an expected AE (for the commercial agent) occurs with a higher degree of severity or specificity, expedited reporting is required.

A list of known/expected AEs is reported in the investigator brochure, package insert or the literature, including AEs resulting from a drug overdose.

10.331 Death

- Any death occurring within 30 days of the last dose, regardless of attribution to an agent/intervention under an IND/IDE requires expedited reporting within 24-hours.
- Any death occurring greater than 30 days with an attribution of possible, probable, or definite to an agent/intervention under an IND/IDE requires expedited reporting within 24-hours.
- **Reportable categories of Death**
 - Death attributable to a CTCAE term.
 - Death Neonatal: A disorder characterized by cessation of life during the first 28 days of life.
 - Death NOS: A cessation of life that cannot be attributed to a CTCAE term associated with Grade 5.
 - Sudden death NOS: A sudden (defined as instant or within one hour of the onset of symptoms) or an unobserved cessation of life that cannot be attributed to a CTCAE term associated with Grade 5.

- Death due to progressive disease should be reported as **Grade 5 “Neoplasms benign, malignant and unspecified (including cysts and polyps) – Other (Progressive Disease)”** under the system organ class (SOC) of the same name. Evidence that the death was a manifestation of underlying disease (e.g., radiological changes suggesting tumor growth or progression: clinical deterioration associated with a disease process) should be submitted.

10.332 Secondary Malignancy

- A *secondary malignancy* is a cancer caused by treatment for a previous malignancy (e.g., treatment with investigational agent/intervention, radiation or chemotherapy). A secondary malignancy is not considered a metastasis of the initial neoplasm.
- All secondary malignancies that occur following treatment with an agent under an IND/IDE to be reported. Three options are available to describe the event:
 - Leukemia secondary to oncology chemotherapy (e.g., Acute Myelocytic Leukemia [AML])
 - Myelodysplastic syndrome (MDS)
 - Treatment-related secondary malignancy
- Any malignancy possibly related to cancer treatment (including AML/MDS) should also be reported via the routine reporting mechanisms outlined in each protocol.

10.333 Second Malignancy

- A second malignancy is one unrelated to the treatment of a prior malignancy (and is NOT a metastasis from the initial malignancy). Second malignancies require ONLY routine reporting.

10.334 Pregnancy

Prior to obtaining private information about a pregnant woman and her infant, the investigator must obtain consent from the pregnant woman and the newborn infant’s parent or legal guardian before any data collection can occur. A consent form will need to be submitted to the IRB for these subjects if a pregnancy occurs. If informed consent is not obtained, no information may be collected.

NOTE: When submitting ACCRU Adverse Event Report reports for “Pregnancy”, “Pregnancy loss”, or “Neonatal loss”, the potential risk of exposure of the fetus to the investigational agent(s) or chemotherapy agent(s) should be documented in the “Description of Event” section. Include any available medical documentation.

10.3341 BMS Reporting: If, following initiation of the investigational product, it is subsequently discovered that a study subject is pregnant or may have been pregnant at the time of investigational product exposure, including during at least 6 half lives after product administration, the investigational product will be permanently discontinued in an appropriate manner (eg, dose tapering if necessary for subject safety).

The investigator must immediately notify [REDACTED] of this event via the Pregnancy Surveillance Form in accordance with SAE reporting procedures.

Follow-up information regarding the course of the pregnancy, including perinatal and neonatal outcome and, where applicable, offspring information must be reported on the Pregnancy Surveillance Form [provided upon request from BMS].

Any pregnancy that occurs in a female partner of a male study participant should be reported to BMS and Seattle Genetics. Information on this pregnancy will be collected on the Pregnancy Surveillance [provided upon request from BMS].

10.3342 Seattle Genetics Reporting: Based on the estimated date of conception, all pregnancies that occur from time of informed consent to within 6 months of last study drug dose, including any pregnancies that occur in the partner of a male study patient, are required to be reported to Seattle Genetics within 48 hours of becoming aware of such pregnancy. Email or fax the Seattle Genetics Pregnancy Report Form to [REDACTED] (USA only toll free). The Seattle Genetics Pregnancy Report Form can be found posted with the protocol on the ACCRU website.

All pregnancies that occur during this time period will be monitored for the full duration; all perinatal and neonatal outcomes should be reported. Infants should be followed for a minimum of 8 weeks.

Abortion, whether accidental, therapeutic, or spontaneous, should be reported as a SAE. Congenital anomalies or birth defects, as defined by the 'serious' criterion above should be reported as SAEs.

